1.0 Background and Rationale

Over the past 35 years the United States Department of Agriculture (USDA) Dietary Guidelines for Americans (DGAs) has sought to translate recommendations on nutrient requirements (i.e., Recommended Dietary Allowances, RDAs) from the Food and Nutrition Board of the Institute of Medicine (IOM) into practical nutritional advice for the American public. In addition to the RDAs, the DGAs are intended to incorporate additional scientific evidence as it arises into the recommendations for a healthy diet.

The lack of appropriate focus on protein nutrition is a major shortcoming of the DGAs. Not only is the amount of protein not a major focus, absolutely no mention is made of protein quality. Protein quality refers to the amount, profile, and true ileal digestibility of the essential amino acids (EAAs) in the protein [1]. The concept of protein quality is not new, as the Protein Digestible Corrected Amino Acid Score was published by the Food and Agriculture Organization of the World Health Organization in 1993. This scoring system was supplanted by the same organization in 2013 by the Digestible Indispensable Amino Acid Score (DIAAS) [1]. In general, animal proteins have much higher DIAASs than plant proteins, often by as much as two fold. Account has not been taken of DIAAS scores, or even the general concept of the importance of the amount and profile of EAAs in individual proteins, in formulation of MyPlate [2] or the scientific report of the DGAs Committee [3]. This is despite the fact that in the IOM report stating the RDA for protein it is specified that this refers to “high quality protein, a classification that does not apply to most plant proteins [4]. The current version of MyPlate continues to disregard the importance of protein quality in the selection of dietary food sources of protein [2]. Under the section in MyPlate titled “Go lean with protein”, it is recommended to “choose from a variety of meat, poultry, seafood, bean and peas, eggs, soy foods like tofu, nuts and seeds”. To help the consumer meet protein needs while achieving the goal of varied protein food sources, the DGAs Committee published “ounce equivalents” in the protein foods group. It is stated among other equivalents cited, that 1 ounce (oz.) of meat is equivalent to 1 tablespoon (Tbsp.) of peanut butter and 1/4 cup (0.5 ounces) of cooked kidney beans [2]. But are they really equivalent? For example, one ounce cooked beef contains 7.8 g of protein and 57 kcal; 1/4 cup cooked kidney beans contains 3.8 g of protein and 56 kcal; and 1 Tbsp. of

reduced fat peanut butter contains 4.66 g of protein and 94 kcal [5]. The inequities of the “ounce equivalents” are even more glaring when protein quality as quantified by the respective DIAASs of animal and plant protein sources is considered. For the examples provided, the DIAAS of beef protein is 117, for kidney bean protein is 59, and for peanut protein is 44 [5]. When account is taken of EAA composition and bioavailability of the protein in each food source according to the DIAAS, it requires consumption of 5 oz. of beef to obtain at least 100% of the daily requirements of all EAAs, whereas it requires 18 cups of cooked beans and 50 Tbsp. of reduced-fat peanut butter. In caloric equivalents, these amounts of food correspond to 10 kcal/kg/day for beef, 33 kcal/kg/day for kidney beans, and 38 kcal/kg/day for reduced-fat peanut butter. The equivalencies have been expressed in the same units as the recommended daily caloric intake defined in the Dietary Reference Intakes as 35 kcal/kg/day [4]. These calculations clearly indicate that the “ounce equivalents” of protein foods in MyPlate are not equivalent in any parameter that might be used to assess nutritional benefit, and demonstrate the bias against animal proteins in the Dietary Guidelines.

The misrepresentation of the equivalencies of various food sources of protein in MyPlate raises the question of the process by which this occurred, and how can the process be influenced to more accurately reflect that high quality of animal proteins? A new DGAs Committee is formed every five years to consider modification of existing recommendations in accord with new information obtained since the last Consultation of the Committee. The Committee not only researches the literature itself for new advances in nutrition research, but holds public hearings in which concerned individuals can make presentations. Publication of new data directly addressing aspects of the DGAs is the most effective approach to sway the Committee to alter a previously-held position.

Developing convincing data to correct the MyPlate “ounce equivalents” of protein foods is an achievable goal. Data from the USDA nutrient data base regarding caloric values and protein content of different protein food sources are helpful in making the argument that the “ounce equivalents” should be adjusted, as are the calculated DIAASs. However, those values are calculated and do not directly reflect functional responses to the “ounce equivalents”. Further, those calculations could have been made before the current DGAs were issued, but if those calculations were made they did not sway the Committee. The most convincing data would be

direct measurement of the physiological responses to “ounce-equivalents” of protein food sources. Dietary protein intake serves many physiological roles, but the most prominent is the maintenance or gain of body protein. This is accomplished by stimulation of protein synthesis, the inhibition of protein breakdown, or a combination thereof. A net gain in protein balance (i.e., synthesis minus breakdown) defines an anabolic response, as opposed to a catabolic response caused by the rate of protein breakdown exceeding the rate of protein synthesis. An anabolic response usually refers to gain of muscle protein, but actually involves the entire body. Thus, the functional response to consumption of a given amount of a protein food source is best assessed by quantifying the rates of protein synthesis and breakdown at the whole body level as well as at the muscle level in order to calculate the anabolic response. We propose to make these measurements in response to intake of “equivalent” (according to MyPlate) amounts of pork, mixed nuts and tofu. Demonstration that the functional responses to these varied sources of protein coincide with the predictions from the USDA nutrient data base and calculation of the DIAAS will provide needed support to redefine “ounce equivalents” of protein food sources according to those data bases for all animal and plant sources of protein.

1.1 Summary of Previous Related Studies

- A.) Essential amino acids (EAAs) are responsible for the anabolic response to protein consumption [6-8].
- B.) Stimulation of muscle protein synthesis in response to EAA is dose-dependent and can be detected with as little as 3 g of free EAA intake.
- C.) Importance of protein breakdown in determining the net anabolic response to protein intake [9].

2.0 Hypothesis

1. Ingestion of 2 ounces of cooked lean pork will induce a greater anabolic response, i.e., increase in the difference between protein synthesis and breakdown, than consumption of either 1 ounce of mixed nuts or 4 ounces of tofu.

3.0 Study Design and Procedures

We will study a total of up to 24 healthy male and females between 18 and 40 years of age. We will use a randomized, two-period, stable isotope (Cambridge Isotope Labs, Tewksbury, Mass.) infusion study: 4.5-hour basal fasted period and 4-hour post-meal period (total 8.5-h time period). The principal end-point will be the total anabolic response (whole body protein synthesis minus breakdown) and the secondary end point will be muscle protein FSR over the 4 hours following the test meal (either pork, mixed nuts or tofu).

3.1 Study Visits

Visit 1: subjects will come to the UAMS IOA 3rd floor for informed consent discussion. Once consent is obtained, subsequent study procedures will be performed. A medical history including allergies and list of current medications will be obtained (printed from Epic if they are a UAMS patient). Subject height, weight, and vital signs will be measured. A blood sample will be drawn for complete blood count [CBC]. A physical exam will be performed at this visit or at visit 2 or 3 at the discretion of the study physician. A DEXA scan for whole-body analysis will be performed in the PI's lab at UAMS (or at visit 2). Subjects can get a copy of their CBC and DEXA scan upon request. Any abnormal findings will be discussed with them by the study nurse and/or physician. Based upon the results of the screening blood sample, visit 2 will be scheduled.

Visit 2: Subjects return to the UAMS IOA. They will be asked about any adverse events since last visit. If not performed at visit 1, the physical exam and/or DEXA scan will be performed at this visit. Randomization will be performed as mentioned below. Subjects will be provided with complete, ready-to-eat meals that they will consume for 3 consecutive days prior to their stable isotope study visit (visit 3). They will be loaned a digital camera to document their compliance for these meals. Visit 3 will be scheduled. See Appendices for menus of the 3 days of meals. Food volume will be tailored for age/sex/body weight so that subjects do not gain or lose weight during the diet run-in period. A UAMS dietician will prepare the specific menus for each

subject, and UAMS Clinical Nutrition staff will prepare and package the meals in the IOA research kitchen located on the 3rd floor of the IOA.

Visit 3: Subjects will return to the IOA having fasted overnight from 10:00 P.M. They will also return their loaner camera. They will be asked about any adverse events since last visit. Study staff will ascertain that subjects complied with the meal requirements prior to proceeding with the stable isotope infusion study. If not performed earlier, the physical exam will be done at this visit.

After vital signs are measured, the study nurse will insert an IV catheter into a vein on each of the subjects' arms. One catheter is used to infuse the stable isotopes L-ring-D5 phenylalanine and 2H2-tyrosine. The other is to allow for frequent blood sampling, warming the arm by means of a heating pad or a heated plastic box. After an initial blood sample is obtained, the study nurse will infuse the priming doses of the two above isotopes as well as a priming dose of 2H4-tyrosine. Constant infusion of isotopes commences immediately after the priming doses are completed. A timer will be started, and blood/muscle samples will be obtained according to the schedule below. The test meal will be served directly after the second muscle biopsy procedure. Subjects will consume 1 serving of one of the test foods: cooked pork loin, mixed nuts or tofu.

At the conclusion of the 8.5-hour infusion study, the IV catheters will be removed and the sites dressed with a sterile bandage. Written and verbal instructions regarding the care of the muscle biopsy site will be provided. A snack and beverage will be offered to subjects. Vital signs will be measured, and subjects will then be free to leave. A follow-up phone call will be made within 72 hours after subjects have left the facility to assess for adverse events related to the stable isotope study visit.

Elapsed time (min)	Procedure
-0	Blood sample (~6mL)
120	Blood sample (~6mL)
150	Blood sample (~6mL), muscle sample (subject's choice of left or right vastus lateralis ~150mg)

180	Blood sample (~6mL)
210	Blood sample (~6mL)
240	Blood sample (~6mL)
270	Blood sample (~6mL), muscle sample (~150mg), ingest test meal
290	Blood sample (~6mL)
310	Blood sample (~6mL)
330	Blood sample (~6mL)
360	Blood sample (~6mL)
390	Blood sample (~6mL)
420	Blood sample (~6mL)
450	Blood sample (~6mL)
480	Blood sample (~6mL)
510	Blood sample (~6mL), muscle sample (~150mg)

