3.2 Subject Compliance

If a subject fails to eat at least 80% of the run-in meals, or fails to completely eat the test meal, they will be dropped from the study.

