3.4 Randomization

We will use permuted block randomization, with random block sizes of 2 or 4, to assign subjects to one of three possible treatment groups. The permuted block design will ensure that group sizes are equal after each block is filled. In addition, the randomization procedure will be stratified by gender to guard against group imbalance. A randomization procedure will be implemented using sealed envelopes, each one being labeled with stratification level (gender) and a label number. The label numbers will be sequential within each of the groups. As a participant is identified and enrolled on study, the study coordinator will ascertain gender, which will determine the set of randomization envelopes to be used. The study coordinator will choose the lowest numbered envelope, which will reveal group assignment. In the event of incomplete subjects that significantly unbalance the groups, subsequent subjects will be randomized into remaining unfilled groups.

A: subjects will consume 2 ounces of cooked pork loin one time during the stable isotope study visit.

B: subjects will consume 1 ounce of mixed nuts one time during the stable isotope study visit.

C: subjects will consume 4 ounces of tofu one time during the stable isotope study visit.

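### Test-meal non-completion is a post-randomization exclusion that can depend on the assigned food and is only partly screened for; randomizing before the run-in check adds further, avoidable exclusions

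*Combined protocol and SAP*

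**What the plan says.** **Test meal.** Section 3.2 sets two grounds for removal. One is eating less than 80% of the run-in meals. The other concerns the test food: a subject who meets the first condition "or fails to completely eat the test meal, they will be dropped from the study". Section 4.2 excludes people allergic to pork, tree nuts or peanuts, or soybeans, and people who do not eat animal proteins. It has no criterion on willingness to eat pork in particular, nuts or tofu.

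**Order of events.** Section 3.1 randomizes at visit 2, before the three days of run-in meals: "Randomization will be performed as mentioned below. Subjects will be provided with complete, ready-to-eat meals that they will consume for 3 consecutive days". At visit 3, "Study staff will ascertain that subjects complied with the meal requirements prior to proceeding with the stable isotope infusion study". The physical exam can also fall there: "If not performed earlier, the physical exam will be done at this visit". The run-in is not described as differing by arm: "Food volume will be tailored for age/sex/body weight". The assignment is first needed at minute 270 of visit 3: "The test meal will be served directly after the second muscle biopsy procedure".

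**Who knows the arm.** Section 3.4: "The study coordinator will choose the lowest numbered envelope, which will reveal group assignment". Section 3.5 lists the principal investigator and the data analysts as blinded, and nobody else.

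**What losses set off.** Section 3.4: "In the event of incomplete subjects that significantly unbalance the groups, subsequent subjects will be randomized into remaining unfilled groups". The word 'significantly' is not defined there.

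**The concern.** Any exclusion after randomization can undo the comparability that randomization provides, if it depends on the arm. Two routes exist here, and they differ in strength.

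The first is the test meal. Whether a subject finishes it can depend directly on which food was served. A person who eats chicken but not pork completes in the nut or tofu arm and is dropped in the pork arm. The analysed groups would then be selected on different food preferences.

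The second is the run-in check and, possibly, a late exam. Both come before the test food, so they depend on the arm only if someone's knowledge of it affects the decision or the subject's behaviour. The present order leaves that open without need. It also turns every run-in failure into an incomplete randomized subject, and such subjects can set off the rule that directs later subjects to unfilled groups.

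**Working it through.** **1. The plan's own figure.** Section 7.2 requires 24 subjects, 8 per food, for 80% power at f = 0.484, with the covariate explaining 50% of the variation and a 5% level. For the ANCOVA F test with 2 and 24 − 3 − 1 = 20 degrees of freedom, the noncentrality is 24 × 0.484² / (1 − 0.50) = 11.24, which gives power of 80.0%. The figure reproduces, and it applies to 24 analysed subjects.

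**2. Test-meal losses.** One non-completer in an arm of 8 is 1/8 = 12.5% of that arm. The documents give no rate of refusal or non-completion for any food, so the number expected per arm cannot be calculated.

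**3. Run-in losses.** No loss rate is given either. Assume a run-in loss p of 5%, 10% or 15%, unrelated to arm, with 8 randomized per arm at visit 2.

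- Mean post-randomization run-in losses: 24 × p.
- Losses per arm follow Binomial(8, p), independently in three arms. Write b(k) for the probability of k losses in one arm. The chance that the largest and smallest counts differ by at least 2 is 1 − { Σ b(k)³ + Σ [ (b(k) + b(k+1))³ − b(k)³ − b(k+1)³ ] }.
- Example at p = 10%: b(0) = 0.4305, b(1) = 0.3826, b(2) = 0.1488, b(3) = 0.0331. The first sum is 0.139. The second is 0.402 + 0.091 + 0.003 = 0.495. The result is 1 − 0.634 = 0.366.
- A difference of at least 3 comes from enumerating all combinations of the three counts in the same way.

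| Assumed run-in loss | Mean losses of 24 | Two arms differ by ≥ 2 | Two arms differ by ≥ 3 |
|---|---|---|---|
| 5% | 1.2 | 14.8% | 1.5% |
| 10% | 2.4 | 36.6% | 8.0% |
| 15% | 3.6 | 51.2% | 16.6% |

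Two thresholds are shown because section 3.4 does not say how large an imbalance counts. If the envelope is opened after the check, run-in losses contribute zero to every column.

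**4. What timing does not change.** To obtain 24 run-in completers, on average 24 / (1 − p) = 25.3, 26.7 or 28.2 subjects must start the run-in, whenever the envelope is opened. Section 4.0 allows up to 30. If all 30 start, the chance of at least 24 completers, from Binomial(30, 1 − p), is 99.9%, 97.4% or 84.7%. The documents do not say whether the margin of 6 must also cover screen failures.

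**The case against.** The case against the timing point is substantial. Run-in failure precedes any exposure to the test food, so removing those subjects biases the comparison only if knowledge of the arm plays a part. Only the coordinator is stated to see the assignment. The compliance assessor, the study physician and the subject are not stated to be blinded or unblinded, and silence is not evidence of unblinding. Discretion is also limited: section 3.2 sets a numeric threshold, and section 3.1 has subjects document their meals with a loaned camera. That a visit 3 exam could lead to exclusion is an inference from the study physician's discretionary criterion in 4.2; the protocol does not say so. The imbalance figures rest on assumed loss rates and fall three- to ten-fold when the threshold moves from 2 to 3. They also count losses at one point, whereas the refill rule acts during accrual. Imbalance from losses unrelated to arm is not itself bias.

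All of this stands, and it makes the timing change a safeguard against a possible bias. It does not show that the early opening serves a purpose: the documents describe no use of the assignment before the test meal.

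On the test meal, it can fairly be said that the servings are small (2, 1 and 4 ounces) and that the allergy and animal-protein criteria already remove many likely refusers. That limits the problem but leaves the gap for pork, nuts and tofu individually.

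**Conclusion.** The point holds as a low-cost improvement. The food-dependent drop rule is the stronger part, because it is the only route tied directly to the assigned food. Each such loss costs one-eighth of an arm, and its frequency cannot be estimated from the documents. The timing part is secondary. It rests on assumed run-in losses of 5% to 15% unrelated to arm, and on an assumed reading of the undefined imbalance threshold.

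A reader might infer more than the documents support:

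- *That the early randomization biases the result.* Nothing shows that anyone deciding on compliance or eligibility knows the arm.
- *That the trial loses power through this order.* The stated power reproduces for 24 analysed subjects, and the number who must start the run-in is the same at either time.
- *That food acceptance is not screened at all.* Section 4.2 screens for it in part.

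**What to change.** 1. **Section 4.2.** Add an exclusion: *Subjects unwilling to eat a full serving of any of the three test foods (pork, mixed nuts, tofu).*
2. **Section 7.1.** Report the number of test-meal non-completers by arm. A sensitivity analysis that includes them is not proposed: section 3.2 drops these subjects, so their post-meal samples may not exist, and that section would have to change first.
3. **Sections 3.1 and 3.4.** State that the envelope is opened at visit 3, only after run-in compliance and all outstanding eligibility checks, including any deferred physical exam, are confirmed and recorded, and before the test meal.

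The cost is wording in four sections, with no added visits or samples. The practical downside is that all three foods must be available on each visit 3 day. Item 3 does not address test-meal losses, which need items 1 and 2. It reduces use of the refill rule in 3.4 without removing it, since infusion-day losses can still set it off.

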3.2 Subject Compliance

If a subject fails to eat at least 80% of the run-in meals, or fails to completely eat the test meal, they will be dropped from the study.

3.3 Subject Compensation

Subjects will accrue compensation for every visit according to the below table. They will be mailed a check for their total compensation approximately 2-3 weeks after their participation ceases (whether completed or not). If they were to attend every visit, their total amount would be \$325. If they quit the study during visit 3, they will receive prorated pay of \$25 per hour.

Visit	Amount
1	\$10
2	\$15
3	\$25 per hour up to \$300

3.4 Randomization

We will use permuted block randomization, with random block sizes of 2 or 4, to assign subjects to one of three possible treatment groups. The permuted block design will ensure that group sizes are equal after each block is filled. In addition, the randomization procedure will be stratified by gender to guard against group imbalance. A randomization procedure will be implemented using sealed envelopes, each one being labeled with stratification level (gender) and a label number. The label numbers will be sequential within each of the groups. As a participant is identified and enrolled on study, the study coordinator will ascertain gender, which will determine the set of randomization envelopes to be used. The study coordinator will choose the lowest numbered envelope, which will reveal group assignment. In the event of incomplete subjects that significantly unbalance the groups, subsequent subjects will be randomized into remaining unfilled groups.

A: subjects will consume 2 ounces of cooked pork loin one time during the stable isotope study visit.

B: subjects will consume 1 ounce of mixed nuts one time during the stable isotope study visit.

C: subjects will consume 4 ounces of tofu one time during the stable isotope study visit.

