4.0 Study Population

Subjects will be recruited using these methods: 1) past subjects that indicated they wanted to be contacted about future studies will be called by study staff to elicit their interest in this study, 2) the study staff will place IRB-approved flyers around the Little Rock community, 3) study staff will engage Research Match.org, and 4) study staff will engage ARResearch program through the UAMS TRI. Once a potential subject has agreed to come to UAMS for an informed consent discussion, an appointment will be made for them to meet with study staff in the research area of the 3rd floor of the Reynolds Institute at UAMS. This study will enroll up to 30 subjects

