7.2 Sample Size Calculation & Power Analysis

A total of N=24 subjects (8 per protein source) will be required for this study. With this sample size, the ANCOVA model will have 80% power to detect effect sizes of $f = 0.484$ or larger (Table 1). This estimate assumes the basal covariate explains 50% of the variation in the response and a 5% α -level is used to determine statistical

Table 1. Expected Effect Size by Covariate Variation

Variation Explained by Covariate (%)	Detectable Effect Size, f
10	0.649
30	0.573
50	0.484
70	0.375
90	0.216

significance. (Note that the effect size, f , is simply the ratio of the variation between the three group means and the between-subject variation). In the event the effect of the covariate is mis-

specified, the following table presents effect sizes that can be detected as the magnitude of variation explained by the covariate increases from 10% to 90%.

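### Permuted blocks of 2 or 4 cannot be equal over three arms, so the balance that section 3.4 promises after every filled block cannot hold

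*Combined protocol and SAP*

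**What the plan says.** Section 3.4 (Randomization) sets the scheme: "We will use permuted block randomization, with random block sizes of 2 or 4, to assign subjects to one of three possible treatment groups". The three groups are pork, mixed nuts and tofu. The following sentence states the property that the blocks are meant to deliver: "The permuted block design will ensure that group sizes are equal after each block is filled". Gender is the stratification factor, with a separate set of envelopes for each gender, and its purpose is given: "the randomization procedure will be stratified by gender to guard against group imbalance".

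Section 7.2 shows that equal allocation is intended: "A total of N=24 subjects (8 per protein source) will be required for this study". Nowhere do the documents give another block size, an unequal allocation ratio, or a rule for making up a block that does not divide by three. Section 3.4 ends with a rebalancing rule, but it applies only when incomplete subjects have unbalanced the groups.

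**The concern.** Two adjacent sentences of section 3.4 cannot both be followed. Equal numbers of three arms fit into a block only when its size is a multiple of 3, and neither permitted size is. Whoever prepares the envelopes must either depart from the stated block sizes or give up the stated balance. They must also invent a way to compose uneven blocks, because the protocol gives none, so the list cannot be reproduced from the document.

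Balance within each gender is at stake, and with it the planned 8 per arm. Stratifying by gender controls imbalance only as far as the blocks inside each stratum do. With about 8 subjects per arm, a difference of 3 or more within one gender is large. Validity of the comparison is not at stake.

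**Working it through.** **Inputs.** Block sizes 2 and 4, three arms, two gender strata (section 3.4). N = 24 with 8 per arm, f = 0.484, covariate R² = 0.50, α = 0.05, stated power 80% (section 7.2).

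**1. The plan's own power figure.** The noncentrality is λ = N f² / (1 − R²) = 24 × 0.484² / 0.50 = 24 × 0.234256 / 0.50 = 11.244. The degrees of freedom are 2 and 24 − 3 − 1 = 20. The noncentral F distribution gives power 0.8003, which agrees with the stated 80%. The calculation takes 8 per arm as given.

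**2. Divisibility.** 2 mod 3 = 2 and 4 mod 3 = 1. No block of either size can be equal over three arms, however it is composed. The count after the first filled block of a stratum is 2 or 4, so equality there has probability 0. This step needs no assumption.

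**3. Later block ends, within one stratum.** Assume the two sizes are equally likely and each block is as even as possible. A block of 2 then omits one random arm, and a block of 4 doubles one random arm.
- After block 2, one block of each size is needed (probability 1/2), and the doubled arm must be the omitted one (1/3): 1/2 × 1/3 = 1/6.
- After block 3, all three blocks must be the same size (1/4), and the three omitted or doubled arms must all differ (6/27 = 2/9): 1/4 × 2/9 = 1/18.
- After block 4, two blocks of each size are needed (6/16 = 3/8), and the two omitted arms must match the two doubled arms (5/27): 3/8 × 5/27 = 5/72.

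With blocks of 3 or 6 the probability is 1 at every block end.

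**4. Effect on the whole list (illustration).** The documents give neither the gender split nor the make-up of an uneven block. The figures below use the filling rule of step 3, 24 randomized, and 20,000 simulated lists for each of the splits 12/12, 11/13, 10/14, 9/15 and 8/16.

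| Outcome (range over splits) | Blocks of 2 or 4 | Blocks of 3 or 6 |
|---|---|---|
| Exactly 8/8/8 | 8-9% | 29-67% |
| Some arm with 6 or fewer | 41-44% | 1-3% |
| Arms differ by 3 or more within at least one gender | 44-59% | 0% |

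Blocks of 3 or 6 do not give 8/8/8 every time, because the last block in a stratum may be left unfilled.

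**5. Effect on power.** Use the inputs of step 1 and average over which arm is short. Power is 0.800 at 8/8/8, 0.797 at 7/8/9 and 0.790 at 6/9/9 (0.73-0.85 at 6/9/9, depending on which means differ). Averaged over lists it is 0.790-0.791 with blocks of 2 or 4 and 0.798-0.799 with 3 or 6, a difference of about 1 percentage point.

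**The case against.** The contradiction itself is not open to dispute. The case on the other side is that it matters little.

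- **Only single blocks are never equal.** Cumulative counts can come out equal, with probability 1/6 after the second block, and the full list can end at 8/8/8. This is correct. The protocol, however, promises equality after every filled block.
- **The analysis does not need equal arms.** The ANCOVA is unbiased with unequal groups, the Tukey-Kramer method in section 7.1 allows for them, and the average power loss is about 1 point. All of this stands and limits the severity.
- **Blocks of 2 or 4 still beat simple randomization.** Under the same filling rule, some arm has 6 or fewer in about 41% of lists, against about 72% with simple randomization. A within-gender difference of 3 or more occurs in about 43-56% against 86-89% (splits 12/12, 10/14 and 8/16). This also stands: the scheme gives partial protection, though not what is promised.
- **The percentages describe randomized lists, not analysed arms.** Section 3.2 drops non-compliant subjects, and section 3.4 may then send later subjects to unfilled groups. The percentages are therefore not forecasts for this trial. That rule is confined to imbalance caused by incomplete subjects and does not repair imbalance built into the list.
- **A larger number should not be read in.** Section 4.0 says "This study will enroll up to 30 subjects", but consent precedes randomization, so enrolled need not mean randomized. The illustration is therefore kept at 24.

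**Conclusion.** The concern holds. Section 3.4 guarantees a property that its own block sizes rule out; this follows from divisibility alone and rests on no assumption. The illustrated loss of balance is substantial: exact 8/8/8 in about 8-9% of lists instead of 29-67%, and a within-gender difference of 3 or more in about 44-59% instead of none. Those percentages depend on 24 randomized, the assumed gender splits and blocks filled as evenly as possible. The inferential cost is small, about 1 percentage point of power on average with no bias. It should be fixed, because the text is wrong as written and the correction is nearly free, but it does not threaten the trial's validity.

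**What to change.** Replace the block sizes in section 3.4 with multiples of 3, for example random sizes of 3 or 6, applied separately within each gender. Reword the balance sentence to say that group sizes are equal within a gender stratum each time a block is filled. Generate the sealed envelopes from a list built that way. How to compose an uneven block then no longer arises.

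This does not guarantee 8/8/8, since a stratum may end partway through a block, but arm sizes within a gender can then differ by at most 2. Deleting the balance sentence alone would remove the contradiction, but it would not restore the balance and would leave the make-up of uneven blocks unspecified.

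The cost is a short protocol amendment and a matching envelope list, with no extra subjects or procedures.
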